9.3.1 Missing and Incomplete Dates

Missing or incomplete date will be listed as it is in any listing. Incomplete start date of an adverse event or concomitant medication taken will be handled by following rule:

	Missing	Imputation	Exception
Start date (AE, concomitant medication)	Day	01	Default to study day 1 if an adverse event starts the same year and month as study day 1 and the flag indicates that the adverse event started on or after the first dose on the adverse events eCRF
	Day/Month	01JAN	Default to study day 1 if an event started the same year as study day 1 and the flag indicates that the adverse event started on or after the first dose on the adverse events eCRF
	Day/Month/Year	No imputation	

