Study Design: This is a multicenter, open-label study designed to assess the long-term safety and efficacy of AMG 334. Subjects who complete the 12-week double-blind treatment phase of the AMG 334 20120295 parent study and meet all AMG 334 20130255 eligibility criteria will be enrolled into the study. Enrollment should occur within 14 days of the week 12 visit of the AMG 334 20120295 parent study. Subjects who enroll in the AMG 334 20130255 study will end the AMG 334 20120295 study and will not participate in the parent study safety follow-up visit. Subjects may also elect to participate in a Novel Patient-reported Outcome Substudy in addition to a CHU substudy.

All subjects who have not yet enrolled in the study will receive open-label AMG 334 140 mg every month (QM) subcutaneous (SC) for 13 months. Subjects who are already enrolled in the 20130255 study will increase the open-label dose from 70 mg QM to 140 mg QM at the first available opportunity at either week 4, 8, 12, 16, 20, 24, or 28 visits. Subjects who have already

completed the week 28 visit will continue to receive 70 mg QM. Subjects will not have the option to decrease open-label AMG 334 from 140 mg QM to 70 mg QM. The 13-month open-label AMG 334 treatment phase will be followed by a 12-week safety follow-up visit (16 weeks after last dose of investigational product).

Sample Size: All subjects who completed the 12-week double-blind treatment phase of the AMG 334 20120295 parent study, meet the inclusion and exclusion criteria for the AMG 334 20130255 OLE study will be eligible to be enrolled. Up to 651 subjects may participate in the study.

Summary of Subject Eligibility Criteria: Adults with history of chronic migraine and who completed the 12-week double-blind treatment phase of the parent study. For a full list of eligibility criteria, please refer to [Section 4.1](#).

Amgen Investigational Product Dosage and Administration: Investigational product (IP) (ie, AMG 334 70 mg or 140 mg) will be dosed QM by SC injection. **For subjects participating in the CHU substudy, IP is AMG 334 140 mg in either a PFS or prefilled AI/Pen.**

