3.1 Study Design

This is a multicenter, open-label study designed to assess the long-term safety and efficacy of AMG 334. Subjects who complete the 12-week double-blind treatment phase (DBTP) of the AMG 334 20120295 parent study and meet all AMG 334 20130255 eligibility criteria will be enrolled into the study. Enrollment should occur within 14 days after the parent study's week 12 visit. **Subjects who enroll in the AMG 334 20130255 study will end the AMG 334 20120295 study and will not participate in the parent study safety follow-up visit.**

All subjects who have enrolled in the study under Protocol Amendment 3 or later, will receive open-label AMG 334 140 mg every month (QM) SC for 13 months. Subjects who enrolled in the 20130255 study, prior to Protocol Amendment 3, will increase the open-label dose from 70 mg QM to 140 mg QM at the first available opportunity at either week 4, 8, 12, 16, 20, 24, or 28 visits. Subjects who have already completed the week 28 visit will continue to receive 70 mg QM.

All subjects will receive open-label AMG 334 QM SC for 13 months followed by a 12-week safety follow up visit (16 weeks after the last dose of investigational product [IP]).

Investigational product AMG 334 70 mg or 140 mg will be dosed QM, SC.

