7.3 Safety Analysis Set

The Safety Analysis Set (SAS) includes all enrolled subjects who received at least one dose of investigational product in study 20130255. Analyses for safety endpoints and

summary of IP administration will utilize this analysis set. The SAS and FAS are the same analysis sets.

Treatment group identifiers for non-AE safety data based the duration of AMG 334 70 mg and 140 mg exposure will be as follows (see [Section 6.6](#)):

- **AMG 334 70 mg**
- **AMG 334 140 mg**
- **AMG 334 70 mg / 140 mg**

Treatment group identifiers for AE safety data, based on the occurrence of the event relative to their treatment period, will be as follows:

- **AMG 334 70 mg**
- **AMG 334 140 mg**

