10.6.1.1 Relationship of AEs to Dose During the OLE Phase

The exposure-adjusted subject incidence of TEAEs (defined in [Section 6.3](#)) will be tabulated by the dose level of AMG 334 that the subject was receiving on the onset date for a specific TEAE. If a subject had his/her dose withheld or didn't receive IP at that dose level on the date of onset for a specific AE, the planned dose level will be assigned. The time of the first occurrence of the TEAE within each dose will determine the dose level. If a subject had multiple occurrences of the same AE both within a dose level, or at different dose levels, only the first occurrence within each dose level will be presented. Incomplete AE start dates will be imputed according to the algorithm defined in [Section 9.3.1](#).

Exposure-adjusted subject incidence of TEAE at a dose level = $(100 * \text{total number of subjects with the TEAE at the dose level}) / \text{total time (years) at risk for reporting the TEAE for subjects exposed at the dose level}$.

Total time (years) at risk for reporting a specific TEAE at a dose level = $\text{sum of all subjects' time (days) at risk for the TEAE at the dose level} / 365.25$.

For those who have experienced the TEAE, the time (days) at risk for reporting the TEAE at the respective dose level = time (days) at the respective dose level before the occurrence of the TEAE. The exposure-adjusted subject incidence of TEAEs will also be tabulated by the combined dose levels of AMG 334 by ignoring the dose level in which the TEAE occurred.

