10.7 Pharmacokinetic or Pharmacokinetic/Pharmacodynamic Analysis

The pharmacokinetic concentration will be summarized with descriptive statistics by visit and treatment group using PK analyses set. Treatment group assignments will follow those specified for the efficacy analysis.

11. Changes From Protocol-specified Analyses

Since most subjects are likely to receive both 70 mg and 140 mg in this study, descriptive summaries on efficacy endpoints will be presented by randomized treatment group in the 20120295 parent study and first dose received in this study, and not by maximum dose as described in the protocol.

Bed days and missed work/school days due to migraine symptoms not summarized since they were not summarized in 20120295 parent study.

12. Literature Citations / References

Fairclough DL1, Cella DF. Functional Assessment of Cancer Therapy (FACT G): non-response to individual questions. Qual Life Res. 1996 Jun;5(3):321-9.

13. Prioritization of Analyses

Summary tables of safety and efficacy will be produced for the use of the annual report and to support publications, if warranted. Therefore, they might be prepared earlier than others.

14. Data Not Covered by This Plan

There are no plans to specifically analyze or summarize the following data points. However, a listing of these data may be presented and/or additional exploratory analyses may be performed should inspection of the data warrant.

- ECG data
- general comments
- population pharmacokinetics
- biomarker

15. Appendices

[figure not shown]

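### Partial AE start dates that span the 70 mg to 140 mg step-up are always assigned to 70 mg, because the earliest-date imputation in SAP 9.3.1 is reused to determine dose at onset

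*SAP*

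**What the plan says.** **Imputation.** SAP 9.3.1 replaces a missing day with the first of the month and a missing day and month with 1 January. There are two exceptions, both conditional on the eCRF flag for onset on or after first dose. With the day missing: "Default to study day 1 if an adverse event starts the same year and month as study day 1". With day and month missing: "Default to study day 1 if an event started the same year as study day 1". A wholly missing date is left as it is.

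**Reuse for dose.** SAP 10.6.1.1 tabulates exposure-adjusted incidence by the dose "that the subject was receiving on the onset date for a specific TEAE" and adds: "Incomplete AE start dates will be imputed according to the algorithm defined in" section 9.3.1. SAP 7.3 agrees: "Treatment group identifiers for AE safety data, based on the occurrence of the event relative to their treatment period", with a 70 mg and a 140 mg group. SAP 10.6 adds a total.

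**Switching.** SAP 3.1 has earlier enrollees step up "at the first available opportunity at either week 4, 8, 12, 16, 20, 24, or 28 visits". The protocol synopsis closes the other direction: "Subjects will not have the option to decrease open-label AMG 334 from 140 mg QM to 70 mg QM". SAP section 11 expects switching to be the norm: "Since most subjects are likely to receive both 70 mg and 140 mg in this study".

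Neither SAP section has a rule for a partial date that could fall on either side of the first 140 mg dose, and no sensitivity analysis is planned for such dates.

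**The concern.** Taking the earliest possible date is a sensible way to protect treatment-emergent status, because it avoids losing events that might have followed the first dose. For dose attribution the same choice is not neutral. Every switcher takes 70 mg first, so the earliest possible date is a 70 mg date whenever the window of possible onsets crosses the step-up.

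The denominator adds to the effect. Under SAP 10.6.1.1, a subject with the event contributes only the time at that dose before onset. An event set to Study Day 1 therefore adds a case to 70 mg with about zero time at risk. Unless the subject has the same event again on 140 mg, all of that subject's 140 mg time stays in the denominator with no event.

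AE incidence is the primary endpoint. Protocol 2.3 gives additional six-month and one-year safety data as the reason for raising the dose. AE summaries are also part of the possible interim analysis for a regulatory submission (SAP section 8).

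**Working it through.** The plan states no figure on this point, so there is none to reproduce. The check applies the rule to every possible onset day.

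**Inputs from the documents**
- Imputation rule: SAP 9.3.1.
- Step-up at week w = 4, 8, ..., 28: SAP 3.1.
- TEAE window to last dose + 112 days: SAP 6.1.1 and 6.4. With the last dose at week 48 (target day 337), this ends on day 337 + 112 = 449.

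**Assumptions**
- Onset is uniform over days 1 to 449.
- Study Day 1 is spread over a calendar year.
- Onsets after the last dose count under 140 mg in switchers.

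**Direction.** The imputed date is never later than the true date. A true 140 mg onset can move to 70 mg when the imputed date precedes the switch. A true 70 mg onset cannot move to 140 mg. No scenario produced a move in that direction.

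**Share of true 140 mg onsets moved, among AEs with that kind of partial date**

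| Missing part | Mean, week 4 switch | Mean, week 12 | Mean, week 28 | Range by calendar date, all switch weeks |
|---|---|---|---|---|
| Day only | 3.5% | 4.0% | 5.9% | 0% to 12% |
| Day and month | 43% | 50% | 65% | about 0% to 100% |

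With only the day missing, the AEs at risk are those in the single calendar month of the step-up. If the step-up falls on day d of a 31-day month, (32 − d)/31 of the possible days are on 140 mg: 22/31 = 71% for d = 10, 4/31 = 13% for d = 28, and 16/31 = 52% averaged over d = 1 to 31. With the month also missing, the AEs at risk are those in the year of Study Day 1, or in the following year if the step-up comes after 1 January of that year.

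**Effect on rates (illustration; N, the rate r and the fractions f are not in the documents).** Take N = 400 switchers, a true rate r = 0.30 per subject-year at both doses, and a week 12 switch. Then t70 = 84/365.25 = 0.230 years and t140 = 365/365.25 = 0.999 years.
- 70 mg: events = 400(1 − e^(−0.069)) = 26.7; subject-years = 26.7/0.30 = 88.9.
- 140 mg: events = 400(1 − e^(−0.300)) = 103.6; subject-years = 103.6/0.30 = 345.4.
- Let f be the fraction of onsets lacking day and month. With f = 5%, events moved = 0.05 × 0.503 × 103.6 = 2.6.
- New 70 mg rate: of the 2.6, about 2.6 × e^(−0.069) = 2.4 subjects have no 70 mg event already. Their 70 mg time falls to about zero, a loss of 2.4 × 0.230 = 0.56 years. The rate is (26.7 + 2.4)/(88.9 − 0.56) = 32.9 per 100 subject-years.
- New 140 mg rate: each moved event returns on average 0.52 years at risk. The rate is (103.6 − 2.6)/(345.4 + 2.6 × 0.52) = 29.1.

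| Partial dates | 70 mg | 140 mg |
|---|---|---|
| 2% lack day and month | 31.2 | 29.7 |
| 5% lack day and month | 32.9 | 29.1 |
| 10% lack day and month | 35.9 | 28.3 |
| 10% lack day only | 30.4 | 29.9 |

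At a week 28 switch, the 5% day-and-month case gives 31.2 against 28.9.

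**The case against.** **The effect may be too small to matter.** AEs are recorded at every monthly visit (Protocol Table 1), onset dates are required (Protocol 9.2.1), and omissions are checked and queried (Protocol 12.3). The missing-data text in SAP 9.3 mentions only the day portion. A month should rarely be lost, and the day-only effect is negligible. This stands, and it limits the weight of the point. It does not remove it, because SAP 9.3.1 makes explicit provision for missing months and the count is unknown.

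**The study estimates and does not test.** SAP sections 5 and 10.6 rule out hypotheses and comparisons between dose groups. True, but the by-dose rates will still be read side by side.

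**Attributing to 140 mg only reverses the bias.** This also stands. With a step-up on the 28th, an AE dated only by that month would go to 140 mg although 27 of its 31 possible days are on 70 mg. Placing onset on the first 140 mg dose date also gives zero time at risk, this time at 140 mg. This is why both attributions should be shown.

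**Stronger readings to avoid.** A reader might infer that every AE of uncertain onset in a switcher goes to 70 mg. The rule changes the column only when the known date parts straddle the step-up and the true onset came after it. A reader might also take the share of the 52 weeks spent on 140 mg as the misassignment rate: 1 − 4/52 = 92% down to 1 − 28/52 = 46%. That is a share of exposure, not of misplaced events. Nor do wholly missing dates go to 70 mg: they are not imputed, so their dose column is undefined.

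**Conclusion.** The point holds in a limited form. For switchers, the two SAP sections together send every straddling TEAE to 70 mg. The bias goes one way, and nothing else in the documents corrects it.

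Its size cannot be stated, because the documents do not give the number of partial dates. Under uniform onset, about 3.5% to 5.9% of true 140 mg onsets move on average among AEs missing only the day, which is probably negligible overall. Among AEs missing the month as well, the average is about 43% to 65%. Whether that shifts the by-dose rates visibly depends on how many such AEs there are.

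Subjects who received one dose cannot be put in the wrong column. Subject counts in the total AMG 334 column do not change, although an earlier imputed onset shortens time at risk there too. The documents do not support a claim that the overall primary result is distorted, or that the 140 mg rate is materially understated.

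**What to change.** Amend SAP 9.3.1 and 10.6.1.1 before database lock:

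1. Keep the present imputation for treatment-emergent status.
2. For dose attribution only, define the window of possible onset dates from the known date parts, the first-dose flag, the AE end date and the end-of-study date. If the window includes the first 140 mg dose date, attribute the TEAE to 140 mg in the by-dose table as a stated conservative convention. Also state which date stops the time at risk.
3. Show the by-dose rates again with the 9.3.1 attribution (70 mg) as the opposite bound.
4. Footnote the number of straddling AEs. If it is near zero, the footnote settles the matter.
5. List AEs with wholly missing start dates separately and keep them in the total column, without inventing an onset date.

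The cost is a small amount of extra programming and one further presentation of the by-dose table. The downside is that a few true 70 mg events will count under 140 mg in one of the two presentations.

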9.3.2 Missing Baseline Evaluation

Refer to 20120295 study SAP Section 9.3.2 “Missing Baseline Evaluation”, on how to handle missing 20120295 parent study baseline.

For 20130255 study baseline, for variables other than monthly rate or monthly average of migraine and non-migraine headache related efficacy endpoints (**including secondary efficacy endpoints, monthly migraine attacks, monthly headache, monthly moderate and severe headache, monthly average severity of migraine pain and monthly average severity of migraine related symptoms**), unless otherwise defined, baseline value is the last non-missing assessment taken during the last 4 weeks (week 8 through week 12) of the parent study 20120295. If it is still missing following above definition, then baseline evaluations will not be imputed and will be considered as missing. For safety endpoints, 20130255 study baseline is the last non-missing measurement (**including measurements from the 20120295 parent study**) before day 1 IP dose in the study 20130255.

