6.3 Study Points of Reference

Baseline

There are two baselines for this study: one is based on the 20120295 parent study baseline and other is based on the 20130255 study baseline.

The 20120295 parent study baseline is the baseline defined in the 20120295 parent study. For monthly efficacy endpoints, the baseline is derived using the parent study data from the first day subject used eDiary in baseline phase at week-4 study visit through the day prior to study day 1 of the parent study 20120295. For safety endpoints, the baseline is the last non-missing assessment for the endpoint of interest taken before day 1 IP dose in the parent study 20120295.

In addition, for monthly rate or monthly average of migraine and non-migraine headache related efficacy endpoints, 20130255 study baseline is also used and derived using the parent study 20120295 month 3 data (ie, week 8 through week 12 data). For safety endpoints, 20130255 study baseline is the last non-missing measurement (including measurements taken from 20120295) for the endpoint of interest taken before day 1 IP dose in the study 20130255. For C-SSRS, all individual items from the parent

study 20120295 week 12 visit will be used as 20130255 study baseline if available, **otherwise baseline as defined in the parent study will be used.**

Study Day 1

Study day 1 is defined as the first IP dose date in the study 20130255. For subjects who are enrolled but not dosed after enrollment, the study day 1 is defined as the date of enrollment.

Study Day

Study day is defined as the number of days from study day 1.

Before study day 1:

$$\text{Study day} = (\text{date of Interest} - \text{date of study day 1})$$

On or after study day 1:

$$\text{Study day} = (\text{date of Interest} - \text{date of study day 1}) + 1$$

The day prior to study day 1 is -1.

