- **Change from baseline in pain interference with daily activities and migraine-specific impact, as measured by the PROMIS Pain Interference Scale short form and single pain and migraine symptom interference questions**
- **Change in physical impairment over time as measured by the MPFID**

- **Change in impact on everyday activities over time as measured by the MPFID**

Other endpoints

- change from baseline in monthly acute medication treatment in days
- change from baseline in monthly average migraine symptoms interference scale

Percent Change from Baseline

The change from baseline divided by baseline and multiplied by 100:

$$(\text{post-baseline} - \text{baseline}) * 100 / \text{baseline}$$

If the baseline value is 0, then the percent change from baseline is set to be missing. Percent change from baseline in monthly migraine days which is used to determine 50%, 75%, and 100% responder will be calculated as above.

Subject Incidence

The subject incidence for a given event in a given period is defined as the number of subjects with at least one reported occurrence of the event divided by the number of subjects who entered that period. For subjects with multiple occurrences of the same event, the event will only be counted once per subject.

Exposure-Adjusted Subject Incidence

The **exposure-adjusted subject incidence in a given period** is defined as the number of subjects with at least one reported occurrence of the event in a given time period of follow-up divided by total subject years of follow-up in that period. **For subjects with events, only the time until the first event contributes to the total subject years of follow-up. This rate will be presented per 100 subject years.** For subjects with multiple occurrences of the same event, the event will be only counted once per subject. Please refer to the table of safety analysis study windows in [Section 6.4](#) to calculate follow-up time in days for each subject.

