9.3 Handling of Missing and Incomplete Data

Subjects may miss specific data points for a variety of causes. In general, data could be missing due to a subject's early withdrawal from study, a missed visit, or inability to evaluate an endpoint at a particular point in time. For this study, most of the efficacy endpoint will be collected via eDiary and subjects could miss entering several days of data **in between exposures to IP**. The general procedures outlined below describe what will be done when a data point is missing.

Missing eDiary data in the calculation of monthly measurements about subjects' migraine and non-migraine headaches will be handled **using method below**. Unless otherwise specified, all the final analysis and sensitivity analysis will use monthly measurements calculated as follows:

1. **For monthly intervals with ≥ 14 days of eDiary days (days subjects use eDiary and including retrospective eDiary days) in each interval:**
 - a) Monthly frequency measurements (including migraine days, headache days, migraine attacks, cumulative hours of migraine headaches, cumulative hours of migraine headaches with severe pain, acute medication use, etc.) will be

prorated to 28-day equivalents. **Prorated result does not need to be rounded.**

- b) Monthly average severity of migraine pain, migraine related symptoms, **physical impairment scores and impact on everyday activities scores as measured by MPFID** and monthly average scale of migraine interference with daily activity will be calculated as the average of observed scores.
2. **For monthly intervals with < 14 days of eDiary use (including retrospective eDiary days)**, all monthly measurement will be set as missing and will be handled as described in [Section 9.3.2](#)

An information day is a calendar day which is either an eDiary day or headache day and will be used toward headache day proration. The eDiary days will be used toward migraine day proration and medication use day proration.

Missing PROs (MSQ, MIDAS) collected at office visit at certain assessment will not be imputed.

Missing safety endpoints will not be imputed. **Missing day portion of AE start time will be imputed based on [Section 9.3.1](#).**

Missing pharmacokinetic and antibody data will not be imputed.

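### SAP 9.3.2 conflicts with SAP 6.6 and 9.3 on the month 3 baseline of the daily MPFID and migraine symptom interference scores

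*SAP*

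**What the plan says.** SAP 6.3 sets up two baselines: the parent-study baseline, and a 20130255 baseline taken from the end of the parent study. On the second it says that "for monthly rate or monthly average of migraine and non-migraine headache related efficacy endpoints, 20130255 study baseline is also used", derived from the parent data of weeks 8 to 12. The protocol glossary calls these the parent study Month 3 data.

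SAP 9.3.2 then covers the rest. Its rule is "for variables other than monthly rate or monthly average of migraine and non-migraine headache related efficacy endpoints" and, "unless otherwise defined", the "baseline value is the last non-missing assessment taken during the last 4 weeks (week 8 through week 12) of the parent study 20120295". The parenthesis describing the excepted group names the secondary efficacy endpoints, migraine attacks, headache, moderate and severe headache, pain severity and symptom severity. It does not name the MPFID, the symptom interference items or PROMIS. Safety endpoints have their own rule.

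SAP 9.3 item 1(b) applies to monthly intervals with at least 14 diary days. Under it, "physical impairment scores and impact on everyday activities scores as measured by MPFID" are averaged over the observed scores, and the "monthly average scale of migraine interference with daily activity will be calculated as the average of observed scores".

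SAP 6.6 defines change as the monthly measurement minus a baseline measurement that is also monthly. The endpoints placed under that formula include the MPFID and PROMIS/interference endpoints and "change from baseline in monthly average migraine symptoms interference scale".

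Protocol 7.2.1.10 and 7.2.1.15 have the MPFID and the interference items completed every day in the diary periods. PROMIS is weekly, and 7.2.1.12 gives it a 7-day recall. The MSQ and MIDAS are completed in the clinic at scheduled visits.

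**The concern.** For an instrument completed daily, a last assessment is one day's score, while the value it is subtracted from is a mean of 14 to about 28 days. Migraine is episodic, so one day says little about the level of the month. Much of the resulting change would reflect what kind of day the last one was.

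Two programmers who start from different sections would derive different baselines for the same table. The comparison at stake is change from parent month 3, which protocol 10.4.1 says will be evaluated and SAP 10.1 says may be.

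**Working it through.** The plan states no figure on this point, so there is nothing to reproduce. The check has two parts.

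**Setting the sections side by side**

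- The 9.3.2 rule is a definition and not only a fallback. After stating it, the section goes on to say what happens if the value is still missing under it.
- MPFID and symptom interference are absent from the endpoints named as excepted. On a literal reading they get one last assessment.
- SAP 6.6 requires a monthly quantity on the baseline side for these endpoints, and 9.3 item 1(b) says how a monthly value is formed. On that reading they get a week 8 to 12 average.
- SAP 9.3 item 2 sets a month with fewer than 14 diary days to missing and refers the reader to 9.3.2. Even someone who follows 6.6 could then replace a month just declared missing with a single day.

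**Size if 9.3.2 is followed (illustrative)**

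The documents give no SD or correlation for these scores, so every input here is assumed. Take a daily score as a subject-month level plus day noise, with total variance 1. Let ICC be the share of variance in the level (0.3 to 0.7), rho the day-to-day autocorrelation (0 to 0.6), and r the correlation of levels between months (1.0 or 0.8). Noise in the two periods is treated as independent. Write w = 1 − ICC.

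- Drift between months: D = 2 × ICC × (1 − r).
- Noise variance of an n-day mean, per unit of w: V(n) = [n + 2 Σ (n − k) rho^k] / n², summed over k = 1 to n − 1.
- One-day baseline: variance of change = D + w + w V(28).
- Monthly baseline: variance of change = D + 2 w V(28).

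Three cases:

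- *Largest ratio.* r = 1, rho = 0, ICC = 0.5. V(28) = 1/28. One-day: 0.5 × (1 + 1/28) = 0.518, SD 0.720. Monthly: 0.5 × 2/28 = 0.036, SD 0.189. Ratio 3.81, which is √14.5.
- *Middle.* r = 0.8, rho = 0.3, ICC = 0.5. D = 0.2 and V(28) = 0.065. One-day: 0.2 + 0.5 + 0.032 = 0.732, SD 0.856. Monthly: 0.2 + 0.065 = 0.265, SD 0.515. Ratio 1.66.
- *Smallest ratio.* r = 0.8, rho = 0.6, ICC = 0.7. D = 0.28 and V(28) = 0.133. One-day: 0.28 + 0.3 + 0.04 = 0.62, SD 0.787. Monthly: 0.28 + 0.08 = 0.36, SD 0.600. Ratio 1.31.

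Over the whole grid the ratio runs from 2.06 to 3.81 with no drift (r = 1.0) and from 1.31 to 2.23 with r = 0.8. Using 14 post-baseline days instead of 28 matters little: in the middle case the one-day SD goes from 0.856 to 0.874.

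A second assumed setting falls inside that range: a 0 to 100 scale, independent days and a month-to-month SD of 5, so that drift adds 2 × 5² = 50.

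- Daily SD 10: 100 + 100/28 + 50 = 153.6 (SD 12.4) against 200/28 + 50 = 57.1 (SD 7.6), ratio 1.6.
- Daily SD 20: 400 + 400/28 + 50 = 464.3 (SD 21.5) against 800/28 + 50 = 78.6 (SD 8.9), ratio 2.4.

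SAP 10.1 asks for a 95% confidence interval of the mean. With the same subjects, its width grows in the same ratio. If the month is stationary, a single day and the monthly mean have the same expectation, so the expected mean change is the same under either baseline.

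**The case against.** The strongest reply is that 9.3.2 yields to any other definition, and that 6.6 supplies one by calling for a monthly baseline. The excepted group is also described as a category with examples, and 9.3 item 1(b) treats the MPFID and interference scores as monthly averages alongside pain and symptom severity. On this view the week 8 to 12 average already applies. In addition, PRO text following the symptom severity definition in SAP 6.1.2 is blacked out, as is the MPFID description in the protocol, and either may hold the rule.

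Much of this stands. A reader might infer that 9.3.2 plainly fixes a one-day baseline. The documents do not support that, because 6.6 points the other way and redacted text cannot be counted as absent. But the reply does not settle the matter. The 6.6 list also contains the MSQ and MIDAS, which are completed at visits and are not averaged over diary days, so being listed there does not clearly override 9.3.2. The examples in 9.3.2 name the severity averages and omit these two instruments.

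A reader might also extend the mismatch to PROMIS. It is weekly with 7-day recall, and no readable rule makes its post-baseline value a monthly average, so a comparison of one day with a month does not describe it. What PROMIS lacks is a stated rule.

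**Conclusion.** The sections conflict for the MPFID scores and the symptom interference items, and the text should be settled before the month 3 comparison is programmed. If 9.3.2 is applied literally, the SD of change and the interval width are about 1.3 to 3.8 times larger than with monthly means on both sides. That range rests wholly on the assumed variances and correlations.

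Two stronger conclusions are not supported.

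- *A false improvement in the mean.* A reader might infer one if scores worsen at the end of the parent dosing interval. The documents give no evidence of this for these scores, and protocol 2.3 describes the 70 mg concentration as sustained beyond 28 days. Bias would need an atypical last day or a trend within the month, and neither is shown.
- *Damage to the main efficacy results.* SAP 10.1 makes the parent-study baseline primary. These endpoints are exploratory, the summaries are descriptive and no tests are planned. SAP 6.6 defines responders on monthly migraine days only, so no responder rate rests on these scores.

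This is a minor point of specification.

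**What to change.** In SAP 6.3 and 9.3.2:

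- State that the 20130255 baseline of the MPFID scores and the migraine symptom interference items is the average over parent weeks 8 to 12, with the same 14-day minimum as later months and in line with 6.6. Limit this to subjects for whom those data were collected, since the documents do not say whether the MPFID was completed in that period.
- State that a baseline month below the minimum stays missing, so that the cross-reference from 9.3 item 2 does not bring back a single day.
- Give PROMIS its own matching baseline and post-baseline rule for weekly scores.
- Keep last assessment for the MSQ and MIDAS.
- If a redacted definition already covers this, cross-refer to it in 9.3.2 instead.

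The cost is a sentence or two and a small programming change, with no new data collection. Some subjects with sparse month 3 diaries would lose a baseline. Even at the smallest assumed ratio, precision would suffer only if more than about 42% did (1 − 1/1.31² = 0.42).
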